- The waveform schedule for placebo treatment patients will consist of turning on the cooling fans and leaving the earpieces unpowered for a ~4-minute period.
- The earpiece tips will be covered with EVA rubber to prevent cooling of the ear canal by the metallic earpieces.

The Placebo Device will look identical to the Treatment Device and *will* show, on its screen, a time-varying waveform similar to that for an active treatment. The y-axis of the plot will be labeled "stimulation intensity" and will not list temperature values (the same will be true for the Treatment Device). A patient receiving a placebo treatment will have the sensation of the earpieces creating some pressure in the ear canals and may feel the earpieces warm up to body temperature. Placebo patients will not undergo material caloric vestibular stimulation since no temperature gradient will be created across the horizontal semicircular canal. (The threshold for therapeutic benefit using CVS has not been established, but even small temperature changes can result in nystagmus (Sedjawidata et al. & Vesterhauge et al.).) The term "CVS" will not be used in describing the Device to any patient and no reference to caloric stimulation will be made. The Device will be referred to as a neuromodulation device and the specific mechanism of action will not be disclosed to patients.

All patients will be told that they may or may not benefit from the Device in terms of

pain reduction and that, further, the point in the 3-month treatment period at which a change may be noticed is unknown and may vary from patient-to-patient – i.e., the treatment duration necessary for a potential reduction in pain is unknown for any particular individual. Patients will be told that they may or may not sense slight pressure from the earpieces, a warming or cooling sensation, or slight nausea or dizziness, especially at the end of the treatment session. At the conclusion of the Treatment Period, patients will be asked to identify which arm they believe they entered (active treatment or placebo).

6) Safety; Vestibular System Examination and Monitoring

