CVS has been used extensively and safely in the practice of medicine since its discovery more than a century ago by [name], a discovery for which he received the Nobel Prize in Physiology/Medicine in 1914. There have been no reports in the literature of adverse events or significant negative side effects associated with CVS. The side effect profile from use of the CVS-M Device is expected to be the same as that associated with diagnostic CVS procedures.

CVS-M acts on the central nervous system via the vestibular organs. This mechanism is distinctly different from most forms of neurostimulation that involve either electrical currents applied directly to a target nerve or region (implanted neurostimulators) or a diffuse current to larger areas of the cortex (TMS, CES, tDCS). CVS is non-invasive and easily employed. The SNS CVS-M Device enables its therapeutic use and utility by controlling thermal induction and providing safeguards that ensure treatments remain firmly within parameters established by the supervising physician.

The Berg Balance test (Berg et al.) is well-established and widely used in clinical settings to asses a person's static and dynamic balance abilities. *Inter alia*, the Test is used to quantify clinical improvement or deterioration in patients -- from evaluation of "normals" to assessment of individuals with a wide range of balance impediments. The long form Test consists of 14 balance- related tasks ranging from standing up from a sitting position to standing on one foot. Each task is graded from 0 - 4, and the final measure is the sum from all elements of the Test:

- 41-56 = low risk of fall
- 21-40 = medium risk of fall
- 0-20 = high risk of fall

The Berg Balance test will provide a consistent and easily administered, task-based scheme for identification and quantification of deterioration, if any, of a subject's balance that could be associated with use of the CVS-M Device. The local clinical coordinators will undergo training on administration of the Berg test prior to the Study. Abnormal findings with the Berg test may lead to a more extensive vestibular assessment evaluation. No unexpected side effects, nor any adverse events, have occurred in prior studies utilizing the CVS-M Device.

7) Pivotal Study Endpoints

• Primary Efficacy Endpoint for the Pivotal Study

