For active-treatment subjects as a group: During the third Month of the Treatment Period, their average total number of Monthly Migraine Headache Days will be lower than their comparable averages derived from the Pre-Treatment Baseline Period.

• Secondary Efficacy Endpoints for the Pivotal Study

- The number of active-treatment subjects having a reduction of 50% or more in Migraine Headache Days during the third Month of the Treatment Period as compared with the Pre-Treatment Baseline Period will exceed the number of placebo-treatment patients having that response rate.
- For active-treatment subjects as a group: During the third Month of the Treatment Period, their average Total Monthly Headache Pain Scores will be lower than their comparable averages derived from the Pre-Treatment Baseline Period.
- For active-treatment subjects as a group: During the third Month of the Treatment Period, their average number of Treated Headaches will be lower than their comparable averages derived from the Pre-Treatment Baseline Period.
- For active-treatment subjects as a group: On average, in comparison with their Pre-Treatment Baseline Period, they will have at the end of the Treatment Period, improvement in scores associated with the Quality of Life and Cognition Assessment measures.

• Safety Endpoint for the Pivotal Study:

The principal safety endpoint for the Study is to verify the absence of material dizziness, with the associated risk of falls, as a consequence of using the active-treatment Device. The Berg Balance test will be used to assess any changes in balance performance as a result of Device usage. Transient nausea and minor dizziness may be experienced by patients, as is sometimes reported in the diagnostic CVS literature, and patients will be trained to verify balance stability after a treatment and before standing up. Previous pilot studies using the Device did not identify nausea or dizziness as side effects attributable to the Device, based on patient self-reporting.

8) Calculating Total Monthly Headache Pain Scores

For each subject the following Total Monthly Headache Pain calculations will be made:

- a. Using the Daily Headache Diary data from the Pre-Treatment Baseline Period, the cumulative Pain Scores for all of the days on which the subject had a Headache during the Month will be calculated; and
- b. For the third Month of the Treatment Period, the cumulative Pain Scores for all of

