• Impact with respect to usage of abortive pain medications and co-morbid conditions such as nausea, dizziness, photophobia and phonophobia will be assessed based on the subjects' Daily Headache Diary entries and the Visit Assessments performed by the Investigators and their designates. An assessment will be made by the blinded Statistician as to whether there is evidence of acute or

sustained alterations in the listed measures and co-morbidities during the Treatment Period as separately compared with the Pre-Treatment Baseline Period.

- Data collected from the Quality of Life and Cognition Assessment questionnaires will be utilized for two purposes. Scoring and analysis will be performed by a single, highly experienced, blinded Neuropsychologist. Analysis first will involve review for safety, with protocols being reviewed for *changes* from baseline on the order of one standard deviation or greater on cognitive measures (using published data) and declines indicating clinical change on affective measures. Triggering during this review will prompt a broader review for consideration of withdrawal due to negative effects. Analysis will then secondarily involve pilot comparisons between Treatment and Placebo groups with respect to *changes* in scores across measures. While the present Study is not powered for detection of treatment effects on cognitive/affective measures, the acquired data can serve as pilot work to identify promising areas for future research.
- The following null hypothesis and alternative hypothesis will be evaluated for the Total Monthly Headache Pain secondary endpoint:
 - "There is no difference between the Total Monthly Headache Pain scores (during the third Month of the Treatment Period as compared with the Month during the Pre-Treatment Baseline Period) when comparing subjects treated with the Treatment Device and subjects treated with Placebo Device."
 - "There is a reduction in Total Monthly Pain scores (during the third Month of the Treatment Period as compared with the Month during the Pre-Treatment Baseline Period) when comparing subjects treated with the Treatment Device and subjects treated with Placebo Device."

10) Quality Assurance Monitor

An independent quality assurance monitor will be used to audit Pivotal Study Sites.

11) References:

ICDH-2: (2004). "The International Classification of Headache Disorders: 2nd edition." Cephalalgia 24 Suppl 1: 9-160.

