- Headache-Free Day shall mean a day on which the subject does not have a Headache that is, a day when the subject has a Headache Pain Score of zero.
- Headache History Questionnaire shall mean a listing of patient history elements relevant to the assessment of her or his migraine headache status.
- Headache Pain Scale shall mean an eleven-point pain measurement scale from zero (no pain) to ten (most intense pain). The pain data will also be mapped onto a four-point (0 3) scale and to a description based on "mild/moderate/severe" categories to facilitate placing this Pivotal Study in the context of other prophylactic pain studies. Patients will be trained on the scale shown below in order to rank their pain on the 11-point scale:

Pain scores will be summarized on a 4-point scale as well (0-3) where the transformation shall be achieved in accord with the graph below:

- Investigators will include:
 - [name], Ph.D., Duke U. Medical Center, Dept. of Medicine-Neurology, Durham, NC
 - [name], Duke U. Medical Center, Dept. of Anesthesiology-Pain Division, Durham, NC
 - [name], Naval Medical Center San Diego, Dept. of Otolaryngology, San Diego, CA
 - [name], FRCP, East Kent University Foundation Hospital Trust, Director/Consultant Physician of East Kent Neurorehab Unit, Kent, UK
 - [name]., Dept. of Psychology, University of Kent, UK
 - [name], Michigan Headache and Neurology Institute, Ann Arbor, MI
 - [name], Carolina Headache Institute, Chapel Hill, NC

- [name], Headache Wellness Center, Greensboro, NC
- **Migraine Headache** In terms of *diagnosis* shall mean (following the ICDH-II guidelines) a Headache that lasts at least four hours, reaches a Pain Score of at least four on the Headache Pain Scale (moderate or severe), is not attributed to another disorder and has at least two of the following characteristics from A and at least one of the characteristics from B, respectively:
 - A: (1) unilateral location; (2) pulsating quality; (3) moderate or severe pain intensity; (4) aggravation by or causing avoidance of routine physical activity (e.g., walking or climbing stairs);
 - B: During Headache: (1) nausea and/or vomiting; (2) photophobia and phonophobia;

For the purpose of the Study, headaches will be classified using the patient's own judgment. Patients will receive instructions on how to differentiate a migraine headache from a non-migrainous headache. Treated Headaches will be considered to be Migraine Headaches.

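### Nausea is assessed only as a change from baseline, without separating migraine days or comparing arms, so avoided migraine nausea can offset nausea caused by the device

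*Combined protocol and SAP*

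**What the plan says.** In Section 9, the part on additional safety assessments and Secondary Endpoints says that "co-morbid conditions such as nausea, dizziness, photophobia and phonophobia will be assessed based on" diary entries and the Visit Assessments. The blinded Statistician then looks for evidence of acute or "sustained alterations in the listed measures and co-morbidities during the Treatment Period as separately compared with the Pre-Treatment Baseline Period". That is the only comparison named for these symptoms. No rule separates migraine days from other days, no rule attributes a symptom to migraine or to treatment, and no contrast between arms is given.

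Elsewhere nausea appears in two roles:

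- As a migraine symptom. Criterion B in the Definitions (Migraine Headache) reads "During Headache: (1) nausea and/or vomiting; (2) photophobia and phonophobia". Dizziness is not listed there.
- As a possible effect of treatment. Under Section 5 patients are told they may or may not sense "slight nausea or dizziness, especially at the end of the treatment session". The Safety Endpoint in Section 7 says "Transient nausea and minor dizziness may be experienced by patients, as is sometimes reported in the diagnostic CVS literature". Section 6 adds: "The side effect profile from use of the CVS-M Device is expected to be the same as that associated with diagnostic CVS procedures". Section 7 also records that the pilot studies, on self-report, did not attribute nausea or dizziness to the device.

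Dizziness has a further safeguard: it is the subject of the principal safety endpoint, measured with the Berg Balance test. Nausea has no separate safety analysis.

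**The concern.** One symptom has two sources that an effective device would move in opposite directions. Fewer migraines mean less migraine nausea; twice-daily vestibular stimulation may add nausea of its own. An undivided comparison with baseline gives the net of the two. A report of no increase in nausea could then mean either that the device causes none or that it causes about as much as it prevents, and a reader could not tell which.

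Adding the placebo arm to an all-day total does not resolve this. If the device works, migraine nausea falls further on active than on placebo, so the offset remains in the difference between arms.

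**Working it through.** **The plan's own figure.** The documents state no nausea or dizziness rate, so there is none to reproduce. The responder rates used below come from the Section 9 sample-size table, which does reproduce. With the pooled two-proportion formula, 80% power and two-sided alpha 0.05 (alpha is not stated, so this is an assumption), the six rows give 72, 54, 44, 50, 40 and 32, matching the table. That table is not in dispute.

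**Inputs from the documents**

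- Month: 28 days (Definitions).
- Baseline migraine days, m: 4 to 14 (Section 2).
- Responder: at least a 50% reduction in Migraine Headache Days (Section 9).
- Responder rates: 45-55% active, 10-15% placebo (Section 9).

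**Inputs assumed**

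- q, the share of migraine days with nausea.
- d, the fractional reduction in migraine days.
- r, the rate of device-caused nausea on non-migraine days.
- Background nausea on non-migraine days is set to 0, and device-caused nausea on migraine days is ignored.

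**Step 1: change from baseline, as the plan specifies.**

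Baseline nausea days = m × q.

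On-treatment nausea days = m(1 − d)q + r[28 − m(1 − d)].

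Take a patient who just meets the responder definition: m = 8, d = 50%, q = 0.6.

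- Baseline: 8 × 0.6 = 4.8 days.
- On treatment, migraine nausea: 4 × 0.6 = 2.4 days. Non-migraine days: 28 − 4 = 24.
- r = 5%: 2.4 + 1.2 = 3.6. The total falls although the device caused 1.2 nausea days.
- r = 10%: 2.4 + 2.4 = 4.8. The total is unchanged although the device caused 2.4 nausea days.
- r = 15%: 2.4 + 3.6 = 6.0. Only here does the total rise.

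Split by day type, the r = 10% case shows non-migraine-day nausea rising from 0 to 2.4 days.

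The break-even rate is r = dmq / [28 − m(1 − d)]. Over m = 4-14, d = 25-50% and q = 0.4-0.8 it runs from 1.6% (0.4 ÷ 25) to 26.7% (5.6 ÷ 21) of non-migraine days, which is 0.4 to 5.6 device-caused nausea days offset per Month.

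**Step 2: difference between arms on all-day totals.** Assume responders improve by exactly 50% and the arms do not differ among the others. The responder difference is 45 − 15 = 30 points at the least and 55 − 10 = 45 points at the most. Extra migraine days avoided on active = responder difference × 0.5 × m. Masked nausea days = that × q, with q = 0.5-0.7.

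| m | Extra migraine days avoided | Masked nausea days per 28 |
|---|---|---|
| 4 | 0.6 to 0.9 | 0.3 to 0.6 |
| 8 | 1.2 to 1.8 | 0.6 to 1.3 |
| 14 | 2.1 to 3.15 | 1.05 to 2.2 |

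The overall range is 0.30 × 0.5 × 4 × 0.5 = 0.3 to 0.45 × 0.5 × 14 × 0.7 = 2.2 days.

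**Step 3: which denominator the split needs.** Suppose background nausea occurs on 5% of non-migraine days in both arms and the device causes none. A patient with 4 migraine days has 24 × 0.05 = 1.2 such days per 28; one with 8 has 20 × 0.05 = 1.0. A count per 28 days would therefore show a false excess in the more effective arm. The proportion of non-migraine days is 5% in both.

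**The case against.** The text says symptoms are assessed; it gives no counting rule. The search for acute alterations could cover session-linked effects, and the diary records treatment times. This stands in part: the plan does not prescribe a misleading count. But the one comparison it names is with baseline, and nothing in it separates the two sources.

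The diary is not the only route. Visit Assessments feed the same analysis, coordinators interview subjects at each clinic visit, and adverse events are among the areas to be covered (Section 4(v)). This stands: a reader might infer that device-caused nausea will necessarily be concealed, and the documents do not support that.

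A reader might also extend the point equally to dizziness and falls. The documents do not support that either. Dizziness is not in the migraine definition, patients with vestibular migraine or diagnosed vestibular dysfunction are excluded, and the Berg endpoint addresses balance directly. A narrower gap remains: Berg testing at the start of baseline, about two weeks and study end can miss transient dizziness after home sessions.

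Timing weakens the masking early on. The Background says benefit need not begin at once, so early sessions may show nausea before migraine days fall. However, no time-specific symptom analysis is planned.

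Finally, non-migraine days are a subset shaped by treatment after randomisation, and patients classify their own migraines. Device nausea could itself move a day into the migraine group. This is a sound objection to making the split the only safety result, though not to adding it.

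**Conclusion.** The concern holds for nausea. As planned, the comparison can read as no increase while the device causes nausea, and an all-day placebo comparison alone would not correct it. Under the Step 2 assumptions, about 0.3 to 2.2 nausea days per 28 could be masked between arms (0.6 to 1.3 at 8 baseline migraine days). The size depends on assumed nausea rates and on how far responders improve. If responders lost 75% of their migraine days instead of 50%, the extra days avoided at m = 8 would be 0.30 × 0.75 × 8 = 1.8 to 0.45 × 0.75 × 8 = 2.7.

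A reader might assume that 2 to 4 more migraine days a Month are prevented on active than on placebo. With responders at exactly 50%, the planning rates reach 2 days only from about 9 baseline days upward (2 ÷ (0.45 × 0.5) = 8.9) and never reach 4.

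The primary endpoint is unaffected. What is at risk is the meaning of a reassuring nausea result.

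**What to change.** In the Section 9 text on additional safety assessments:

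1. Keep the all-day nausea comparison as the measure of net burden, but report it by arm, as active minus placebo with a 95% CI.
2. Add a pre-specified safety analysis of nausea, and secondarily dizziness, on days that are not Migraine Headache Days. Express it as the proportion of non-migraine diary days with the symptom, not as a count per 28 days. Report it by arm with a 95% CI and the baseline rate alongside.
3. Report migraine-day nausea by arm as well, and do not treat it as an efficacy description only, since the device may also cause nausea on those days.
4. Confirm that the diary records nausea and dizziness every day. Its definition names only maximum pain and treatment times, and the forms are not in the text available.

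The cost is a few lines of analysis wording and a day-level tabulation of diary data. If the diary does not already ask about both symptoms daily, those items must be added. The split has the limits noted above, so it is read beside the all-day result and does not replace it.

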If the subject is discontinued from the participation in the study for any reason, the Investigator must make every effort to perform all evaluations for the final visit and document the reasons for discontinuation.

• Concomitant Medications

- The use of acute abortive medications for the symptomatic treatment of migraine headache will be allowed during the clinical trial. Subjects may use their usual acute abortive medications, and medications should not be changed during the clinical trial. A Treated Headache will be a Migraine Headache for which a patient has taken an acute abortive medication.
- The patient may be on a single migraine prophylactic as long as the dosage has not been altered within three months of starting the Study and the dosage must not be altered for the duration of the Study. The patient must not have failed on more than two classes of properly administered prophylactic pharmaceutical therapies for migraine headache. Prophylactic medications used to treat other medical conditions may be used, at the Investigator's discretion, if the subject is taking a stable dose for at least three months prior to screening and continues throughout the study.

3) Pivotal Study Size; Randomization

The design size contemplates enrolling up to eighty (80) patients who will successfully follow through to completion of their participation in the Pivotal Study. Half of these patients will be assigned a Treatment Device, and half will be assigned a Placebo Device. Whether a patient is in the treatment arm or placebo arm will be decided randomly based on an assignment within a sealed envelope, which will be opened only by the Pivotal Study coordinator at the relevant Pivotal Study site. The envelopes will be randomized as described below and provided to the participating clinics. A given patient and the Investigator will remain blinded as to the arm to which the patient has been assigned. The assessment of the primary endpoints will be completed by a blinded, central Statistician. The patients will be told, within the informed consent document, of the existence of a placebo arm.

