the days on which the subject had a Headache during the Month will be calculated.

At the conclusion of the Pivotal Study, Total Monthly Headache Pain score comparisons will be made for each subject: Pre-Treatment Baseline Period vs. the third Month of the Treatment Period. Additionally, such Total Monthly Headache Pain scores for the active-treatment subjects as a group will be compared with those for the placebo-treatment subjects as a group.

9) Statistical Analysis and Pivotal Study Size

As noted above, an experienced, independent and blinded Statistician will be utilized to analyze and summarize the Daily Headache Diaries for all patients. Also, as noted, a blinded Neuropsychologist will analyze and summarize the Quality of Life and Cognition Assessment data, and a Vestibular System Consultant will perform a blinded analysis and summary of the data from the Vestibular Testing Procedures.

Summary of the analytical methodology to be used for the Primary Endpoints

- No prospective stratification: Based on the inclusion and exclusion criteria, there is no medical reason to stratify the Pivotal Study's episodic migraine population.
- **Statistical method**: The Pearson's chi-square test will be used to evaluate the null hypothesis, which is that "There is no difference between the number of Migraine Headache Days (during the third Month of the Treatment Period as compared with the Month during the Pre-Treatment Baseline Period) when comparing subjects treated with the Treatment Device and subjects treated with Placebo Device."

The corresponding alternative hypothesis is that: "There is a reduction in Migraine Headache Days (during the third Month of the Treatment Period as compared with the Month during the pre-Treatment Baseline Period) when comparing subjects treated with the Treatment Device and subjects treated with Placebo Device."

We seek to power the Study so as to reject the null hypothesis and accept the corresponding alternative hypothesis. The following power calculations are based on probabilities from binomial distributions (2-sided test):

- Assumed efficacy metric (response rate): a reduction of 50% or more in Migraine Headache Days with respect to baseline.
- Assumed range of efficacy measured in the placebo arm: 10-15%
- Assumed range of efficacy measured in the treatment arm: 45-55%

Treatment efficacy	Placebo efficacy	Statistical power	Total minimum
			cohort size
45%	15%	80%	72
50%	15%	80%	54
55%	15%	80%	44
45%	10%	80%	50

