50%	10%	80%	40
55%	10%	80%	32

The ONSTIM (occipital nerve stimulator) study (Saper et al.) recorded a placebo (preset stimulation) efficacy of 6% and a responder rate (reduction of 50% or more in headache frequency) of 39%. Results from the PREMICE study (Cefaly, supraorbital transcutaneous neurostimulation) cited by Lambert listed a placebo efficacy of 12.1% and a responder rate of 37%. Both studies evaluated between 60-70 patients. Therefore, the range of 10-15% for placebo efficacy is felt to be relatively conservative as compared with other recent studies involving neuromodulation devices addressing Migraine Headache. The assumed efficacy rate range for the CVS Device is based on non-statistically significant observations in the two previous Migraine pilot studies. We therefore conclude that a total Study size of 80 patients is likely to be sufficient for the most probable outcomes, as that number exceeds the minimum in the table above for the most likely treatment and placebo efficacy cases. For comparison, Topiramate (Topamax) used as a prophylactic migraine treatment reports responder rates in the 37-54% range and a placebo response in the low 20% range. Therefore CVS-M responder rates in the 45-55% range would be clinically meaningful.

• **Cohort size**: Each of the sites will enroll subjects with an overall goal of 80 patients. Once up to 80 subjects have completed the Pivotal Study successfully, enrollment in the Pivotal Study will be stopped (at least temporarily) and the data will be analyzed and summarized. Using expected levels of efficacy for the Treatment and Placebo Devices, this cohort size will likely be more than adequate to demonstrate statistical significance and reject the null hypothesis. The cohort size is also expected to be adequate to establish the low rate of unanticipated adverse events associated with usage of the Device. The Sponsor may choose to extend the Study, with IRB approval, should it be necessary to increase the patient cohort size.

Summary of analytical methodologies to be used for additional safety assessments and for the Secondary Endpoints:

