- **Treated Headache:** A Migraine Headache lasting at least 30 minutes for which a patient takes an acute abortive medication.
- **Treatment Device** shall mean a SNS CVS-M Device that is fully active and functioning.
- **Treatment Period** shall mean, with respect to each Pivotal Study participant, the three months following the end of the pre-Treatment Baseline Period. The third Month of the Treatment Period shall be the primary period for which efficacy of the SNS CVS-M Device treatments shall be evaluated.
- Vestibular System Consultant will be [name]., U. of Pittsburgh Medical Center, Dept. of Otolaryngology, Pittsburgh, PA.
- Vestibular Testing Procedure shall consist of the administration of the Berg Balance test. The test results will be reviewed by the Vestibular System Consultant (who will remain blinded).

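### Treated Headaches is the only efficacy endpoint with no active-versus-placebo comparison anywhere in the plan, so meeting it cannot separate device effect from placebo response or drift

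*Combined protocol and SAP*

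**What the plan says.** In the combined protocol and SAP, Section 7 (Secondary Efficacy Endpoints) states for the active-treatment group that, in the third Month, "their average number of Treated Headaches will be lower than their comparable averages derived from the Pre-Treatment Baseline Period". The placebo arm does not appear in that endpoint.

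Section 9 has a list headed "Summary of analytical methodologies to be used for additional safety assessments and for the Secondary Endpoints". No item in it names Treated Headaches. The closest one opens with "Impact with respect to usage of abortive pain medications and co-morbid conditions such as nausea, dizziness, photophobia and phonophobia will be assessed" and then asks the blinded Statistician to look for short-lived changes or for "sustained alterations in the listed measures and co-morbidities during the Treatment Period as separately compared with the Pre-Treatment Baseline Period". It states no hypothesis, test or contrast between arms.

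Two entries in the Definitions connect these texts. A Treated Headache is "A Migraine Headache lasting at least 30 minutes for which a patient takes an acute abortive medication", so the endpoint depends on abortive-drug use. The Treatment Period is "the three months following the end of the pre-Treatment Baseline Period", so the Section 9 bullet, read literally, spans all three Months. Section 2 (Concomitant Medications) says "Subjects may use their usual acute abortive medications", without distinguishing the arms.

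**The concern.** The trial is randomized and placebo-controlled, and Section 9 itself assumes that 10-15% of placebo patients will reach a 50% reduction in Migraine Headache Days. Some improvement without active stimulation is therefore expected. An endpoint met by a fall in the active arm alone takes no account of it.

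A positive result could be reported as a secondary efficacy finding while carrying no controlled evidence. Nor can a between-arm test be presumed here, because the plan writes one out for its other endpoints. Correcting the wording of the primary endpoint would leave this gap in place.

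**Working it through.** **1. Which endpoints are compared with placebo?**

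| Efficacy endpoint | Section 7 wording | Between-arm comparison |
|---|---|---|
| Migraine Headache Days (primary) | Active arm, before-after | Section 9: null and alternative hypotheses on Treatment versus Placebo Device |
| 50% responders | Active versus placebo | Section 7 itself |
| Total Monthly Headache Pain | Active arm, before-after | Section 8: active-group scores "will be compared with those for the placebo-treatment subjects as a group"; Section 9: between-device hypotheses |
| Quality of Life and Cognition | Active arm, before-after | Section 9: pilot comparison of the two groups |
| Treated Headaches | Active arm, before-after | None found |

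**2. The plan's own figures.** The only sizing figures are the six cohort sizes in Section 9, for the responder rate in Migraine Headache Days. They reproduce exactly from the pooled two-proportion formula (two-sided 5%, 80% power, no continuity correction). For 45% versus 15%, n per arm = [1.96√(2×0.30×0.70) + 0.842√(0.45×0.55 + 0.15×0.85)]² / 0.30² = 35.4, rounded up to 36, total 72. The other rows give 54, 44, 50, 40 and 32, as printed. The table is not in dispute. It neither sizes nor tests Treated Headaches.

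**3. What a before-after rule does when the device has no effect.** Inputs: 40 active and 40 placebo patients (half of 80 each, Sections 3 and 9); two-sided 5% (two-sided is stated, 5% is assumed); both arms fall by d SDs of the change score (d is assumed).

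- Mean merely lower than baseline, which is all Section 7 literally asks: probability Φ(d√40), by normal approximation.
- Paired test significant in the favourable direction: P(T > t₀.₉₇₅,₃₉), with T noncentral t, 39 degrees of freedom, noncentrality d√40.
- Between-arm test of change: the shared fall cancels, leaving 2.5% in the device's favour for every d.

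| d | d√40 | Mean lower | Paired test favourable | Between-arm test favourable |
|---|---|---|---|---|
| 0 | 0 | 0.50 | 0.025 | 0.025 |
| 0.2 | 1.26 | 0.90 | 0.23 | 0.025 |
| 0.3 | 1.90 | 0.97 | 0.46 | 0.025 |
| 0.4 | 2.53 | 0.99 | 0.69 | 0.025 |
| 0.5 | 3.16 | >0.99 | 0.87 | 0.025 |

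**4. Price of a controlled comparison.** Detectable effect at 80% power, in SDs of change: within the active arm, (1.960 + 0.842)/√40 = 0.44; between arms, (1.960 + 0.842)×√(2/40) = 0.63.

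**The case against.** The Section 9 bullet does not name Treated Headaches. It groups abortive-drug use with nausea, dizziness, photophobia and phonophobia, under a heading that also covers safety. A before-after look across treatment is reasonable for that purpose. This stands: the defect lies in the Section 7 endpoint and in what Section 9 omits, and the bullet itself need not be wrong.

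A reader might also infer three stronger points, which the documents do not support.

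- *That the placebo arm's data are never used.* The bullet draws on the subjects' diaries without limiting them to one arm, Section 9 has the Statistician analyse diaries for all patients, and the separate comparison it mentions could mean by arm. Placebo summaries may well be produced. What is missing is a specified comparison.
- *That the plan fixes a whole-period window for this endpoint.* The Background, Section 4(iii), Section 7 and the Treatment Period definition all point to the last or third Month for efficacy. The bullet's wider window is at most an inconsistency to reconcile, and only if the bullet is meant to govern the endpoint.
- *That migraine-day counts cannot be read without an arm comparison of abortive use.* Under the Migraine Headache definition a treated headache is classed as a migraine, and a Migraine Headache Day needs only 30 minutes, so a headache softened by a drug generally still counts. The worry applies mainly to pain scores.

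Finally, regression to the mean may be small. In a simulation of 4,000 trials on day counts (assumed mean 8, SD 4, entry on an observed 4-14, no decline), the drop was about 0.13 days, or 0.04 SD of change, and about 5% of trials showed a significant fall. Entry does not select directly on Treated Headaches either. The size of the problem therefore rests on placebo response and drift, which the documents do not quantify for this endpoint.

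**Conclusion.** The concern holds in this form: the stated success rule for Treated Headaches is confined to the active arm, and no section supplies a comparison with placebo. This is more than missing detail, because the rule can be satisfied as written by a device that does nothing.

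The 23% to 87% range is conditional on a shared fall of 0.2 to 0.5 SD, 40 patients per arm, and a paired test that the plan does not actually name. With no shared fall, the before-after test is no worse than the between-arm test, at 2.5% in the favourable direction. The consequence is limited to one secondary endpoint with no stated power. The between-arm comparisons of migraine days, responders, pain and cognition are unaffected.

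**What to change.** Change both places, since editing Section 9 alone would leave the active-only criterion standing.

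1. Section 7: restate the Treated Headaches endpoint as active versus placebo.
2. Section 9: add: *Treated Headaches in the third Month will be compared between the active and placebo arms in a model adjusting for the Pre-Treatment Baseline count (two-sided 5%, with 95% confidence interval).*
3. Keep the existing bullet's before-after review of abortive-drug use, nausea, dizziness, photophobia and phonophobia over the Treatment Period, labelled as descriptive and safety analysis. Replacing the bullet outright would lose the symptom review.

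The cost is wording and one model, using the diary entries that Section 9 already relies on for abortive-drug use, with no extra visits or patients. A fall in the active arm alone would no longer meet the endpoint, and sensitivity drops to the 0.63 SD shown above. Baseline adjustment recovers part of this. With equal variances and baseline-to-third-Month correlation r, its variance relative to a change-score comparison is (1−r²)/(2(1−r)) = (1+r)/2. That is 0.65, 0.75 or 0.85 at assumed r of 0.3, 0.5 or 0.7, so the detectable effect becomes 0.626×√0.65 = 0.50, 0.626×√0.75 = 0.54 or 0.626×√0.85 = 0.58 SD of change.
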